# 1 SYNOPSIS

**TITLE: Food Allergen Elimination and a Brief, Therapeutic Exercise for Obesity Reduction**

**OBJECTIVES:**

Primary: The purpose of this study was to determine if removing food allergens alone or combined with a multi-discipline weight loss protocols are effective in obesity reduction.

NAME OF COMPANY: Galveston Clinical Research Foundation

STUDY SITES: Galveston, Texas, USA

METHODOLOGY: Randomized, Controlled, Cross-over Trial

NUMBER of PATIENTS: 18

Inclusion:

- 1) Healthy adults, ages 20 – 75
- 2) Body Mass Index  $\geq 30$

Exclusion:

- 1) Cardiovascular Heart Disease
- 2) Hypothyroid Secretion (Can reapply after Treatment and normal TSH, T3, T4 levels)
- 3) Hypogonadal syndrome (Can reapply after Treatment and normal testosterone levels.)
- 4) CVA, TBI or any neural injury or disease
- 5) Diabetes Mellitus (Type I or II)
- 6) Other weight loss protocols, diets, or medication (30 day wash out)

Randomized Categorization

- N/A

STATISTICAL METHODS:

A Repeated Measures ANOVA will measure changes in weight, body composition, and BMI.

SAFETY:

Serious Adverse Events associated with study procedures (ALCAT Blood draw, dietary changes and 2-minute exercise sessions) will be reported to the IRB within 24 hours and to the FDA as required by IRB.

**2.**

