The dependent variables in that study were changes in weight (pounds) and 'Body Summation' of 10 girth measurements (neck, shoulders, waist, hip, etc.). A 2x2 ANOVA was used to calculate differences. There was a significant difference between groups ( $P < 0.0001$ ), and the mean changes were as follows: Exp = -18.0lbs and -18.7" vs. Control +1.3lbs and +1.7." [16]

Eating natural, unprocessed foods was discussed in a portion size study [13] and Polsen et al examined differences from changing one's diet to natural foods in the New Nordic Diet [40]. They compared the 'Average' diet (control) to the New Nordic Diet (NND) which removed the processed foods and substituted with natural foods (high in fruits, vegetables, fish, and whole grains). In that study 181 obese subjects (mean age 42) were randomly selected to either the NND group or the Average diet for 26-weeks.

The dependent variable was change in weight and there was a significant difference for the NND vs Average group. The NND subjects showed a mean change of -4.7 kg vs the Average group lost only a mean -1.5kg ( $P < 0.001$ ). There were also significant differences seen in Fat change (1.87% difference,  $P < 0.001$ ), Waist circumference (-2.94cm difference,  $P < 0.001$ ), and in Systolic blood pressure (-5.13 mm Hg difference,  $P < 0.001$ ) [40].

These studies show the overlapping benefits from reducing Portion sizes (with greater meal frequency) and Aerobic-surge or brief, high intensity exercise, plus the benefits of eating Natural foods. The **purpose** of this study was to determine if removing food allergens alone or combined with a multi-discipline weight loss protocols are effective in obesity reduction.

This proposed study will have two volunteer, unrandomized groups: Food Allergen elimination (alone) vs. Combined Treatment (Food Allergen elimination + PAN-5). After 90-days the changes will be tested and compared.

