## **3.1 Summary of Potential Risks**

This is a randomized, cross-over study that will not include and invasive treatments methods or pharmaceutical products. The risks in this study are as follows:

- Drawing blood for diagnostic testing by venipuncture is an invasive procedure that may occasionally be associated with adverse events such as pain, bleeding, syncope, or ecchymosis.
- The Aerobic-surge, 2-minute exercise bouts will have potential risks for injuries such as falls, scrapes, bruises, pulled connective tissue injuries, etc. However this risk is no greater than the risk in daily ambulation and activity.

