## **5 INVESTIGATIONAL PLAN**

### **5.1 Endpoints**

#### **5.1.1 Efficacy Endpoints**

This study is a preliminary, case/control study comparing food allergen elimination and food allergen elimination with PAN-5 for metabolic acceleration. The endpoint will be the 90-day completion of this trial

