### **5.3 Discussion of Study Design**

This is an Investigator-Initiated, preliminary case/control study. A

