### 7.2 Method of Assigning Patients to Treatment

All subjects will receive food allergen testing and they can volunteer to also be treated with the PAN-5 protocol.

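### The protocol is labelled a randomized cross-over trial (and elsewhere case/control), but it describes two self-chosen groups over one 90-day period, so the PAN-5 contrast is open to self-selection

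*Protocol*

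**What the plan says.** The Protocol describes its design in three incompatible ways.

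- **Randomized cross-over.** The synopsis has "METHODOLOGY: Randomized, Controlled, Cross-over Trial". The Summary of Potential Risks (the second section numbered 3.1) says "This is a randomized, cross-over study that will not include and invasive treatments methods or pharmaceutical products".
- **Case/control.** Section 5.1.1 says "This study is a preliminary, case/control study comparing food allergen elimination", and section 5.3 says "This is an Investigator-Initiated, preliminary case/control study".
- **Self-chosen groups.** Section 3.1 Introduction says "This proposed study will have two volunteer, unrandomized groups: Food Allergen elimination (alone) vs. Combined Treatment (Food Allergen elimination + PAN-5". Section 7.2 says "All subjects will receive food allergen testing and they can volunteer to also be treated with the PAN-5 protocol". Section 7.3 excludes both blinding and randomization. The synopsis has an entry headed "Randomized Categorization" and marks it not applicable.

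On timing, sections 5.2.1, 5.2.1.1 and 5.2.1.3 end participation and the study at 90 days or three months. On inference, the Introduction says "After 90-days the changes will be tested and compared", and section 11.8.5 sets a significance threshold of 0.05 without saying which comparison it governs. Section 11.1 lists age, gender, ethnicity and duration of obesity as independent variables; treatment group is not among them.

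**The concern.** Food allergen elimination alone versus elimination plus PAN-5 is the only between-group contrast in the study. In a randomized trial, a significant difference on that contrast could be attributed to PAN-5. When subjects choose, it cannot. People who volunteer for five daily exercise bouts and a restructured eating schedule may well be more motivated, and might have lost more weight on elimination alone. None of the variables listed in section 11.1 measures motivation, so adjusting for them would not remove the difference.

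The label matters because the Methodology line and the risk summary are what an ethics reviewer or later reader is likely to rely on. Either would lead that reader to take a PAN-5 difference as randomized evidence. The problem is confined to the between-group contrast and does not concern the change within each group.

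**Working it through.** **Step 1. Compare each label with the features it requires.**

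| Feature | Needed for | Found in the Protocol? |
|---|---|---|
| Allocation by chance | Randomized trial | No: subject's choice (7.2); randomization excluded (7.3); synopsis entry not applicable |
| Two or more treatment periods per subject | Cross-over | No: one 90-day period (5.2.1, 5.2.1.1, 5.2.1.3) |
| Sequences and a switch | Cross-over | No |
| Washout between periods | Cross-over | No: the only washout (synopsis, exclusion 6, 30 days) concerns earlier weight-loss programmes |
| Groups defined by outcome, exposure looked up backwards | Case/control | No: groups are defined by the intervention chosen and followed forward |

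No label is met. The features present are those of a non-randomized, open-label, parallel comparison of two groups.

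Sections 11.5 and 11.6 mention weekly contact through six months. This conflicts with 90 days and could be left over from a two-period plan, but neither section describes a second treatment period, so it does not rescue the cross-over label.

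**Step 2. Illustrate what self-selection could do to a 0.05 test.** The Protocol states no figure that can be reproduced here: it gives no SD, effect size, power or group ratio.

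Inputs from the Protocol: total of 18 subjects (synopsis) or 20 (section 11.2); threshold 0.05 (section 11.8.5). Assumptions: a two-sided two-sample t test on 90-day weight change, no true PAN-5 effect, and a self-selection bias *d* in SD of weight change that favours PAN-5.

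The noncentrality parameter is d / √(1/n₁ + 1/n₂), with n₁ + n₂ − 2 degrees of freedom. The probability of a significant result favouring PAN-5 is the upper tail of the noncentral t beyond the 0.975 critical value. At 9 vs 9, √(2/9) = 0.471, so d = 0.40 gives 0.40/0.471 = 0.85 on 16 df.

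| Assumed bias d (SD) | 9 vs 9 | 10 vs 10 | 12 vs 6 |
|---|---|---|---|
| 0 (nominal) | 2.5% | 2.5% | 2.5% |
| 0.08 | 3.59% | 3.67% | 3.52% |
| 0.16 | 5.05% | 5.25% | 4.86% |
| 0.40 | 12.27% | 13.30% | 11.37% |
| 0.64 | 24.73% | 27.27% | 22.48% |

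A simulation of 400,000 trials at 9 vs 9 gave 3.56%, 5.07% and 24.71% at d = 0.08, 0.16 and 0.64. Counting both tails, larger assumed biases of 0.25, 0.5 and 1.0 SD give 7.9%, 17.0% and 51.3% at 9 vs 9, against 5% nominal.

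**Step 3. Precision of the contrast.** The 95% confidence interval half-width, in pooled SD, is t(0.975, df) × √(1/n₁ + 1/n₂):

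- 9 vs 9: 2.120 × 0.471 = 1.00 SD
- 10 vs 10: 2.101 × 0.447 = 0.94 SD

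**The case against.** Every section that governs conduct agrees, so staff following section 7 could not randomize anyone by mistake. Sections 5.2 and 11.2 call the study a pilot, volunteer allocation is openly declared, and self-selection is a known limit of that choice rather than an error. On this view the defect is wording alone. This stands in part: the design is legitimate and the operative text is clear. But that text contradicts the headline methodology, and nothing in it limits what the comparison may claim.

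A second objection is that no section names a between-group test. The synopsis says only that a repeated measures ANOVA will be used, section 11.1 omits treatment group, and the objective can be read as asking whether each regimen works. It is fair to say that applying the 0.05 rule to PAN-5 joins two sections. The Introduction does, however, announce that the two groups' changes will be tested and compared, and 0.05 is the only threshold given.

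A third is that the bias sizes in the illustration have no source in the Protocol, the test is not the stated ANOVA, and self-chosen groups could be more uneven. At 4 vs 14 the upper-tail range would be 3.4% to 18% and the interval about ±1.20 SD. All of this is true, and the conclusion does not depend on those figures.

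Finally, an analysis plan not shown could provide for descriptive reporting. It could not make volunteers randomized or correct the Protocol's own labels.

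**Conclusion.** The concern holds and must be fixed. The headline claims two properties, randomization and cross-over, that the study does not have, and the case/control label is also wrong. This follows from the Protocol's text alone and rests on no assumption.

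The size of any resulting bias is unknown. Under the stated assumptions (no true effect, t test, bias favouring PAN-5), the chance of a false finding for PAN-5 rises from 2.5% to between 3.6% and 25% at 9 vs 9, for biases of 0.08 to 0.64 SD. The contrast is imprecise in any case, at about ±1 SD with equal groups.

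**What to change.** 1. Replace the design label in the synopsis Methodology line, the Summary of Potential Risks, and sections 5.1.1 and 5.3 with *non-randomized, two-group, parallel pilot study*. Delete the empty randomization entry in the synopsis.
2. At the end of the section 3.1 Introduction and in section 11, add: *The between-group difference in 90-day change will be reported descriptively with a 95% confidence interval and a baseline comparison by group. Because subjects choose their group, it cannot establish a PAN-5 effect.* Limit the 0.05 rule in section 11.8.5 accordingly.
3. Reconcile the six-month contact in sections 11.5 and 11.6 with the 90-day duration in section 5.2.1 and its subsections.

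This is a text-only amendment with no new visits or data. Its price is a weaker claim for PAN-5.

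If the sponsor does intend randomization, the alternative is to amend the Introduction and sections 7.2 and 7.3 so that consenting subjects are assigned 1:1 from a pre-generated list after baseline, to state in section 8.1 which group receives the Aerobic-surge demonstration, and to call the study a randomized parallel-group pilot. This needs an allocation list and subjects willing to accept either group, which may slow recruitment. If a cross-over is really meant, its periods, sequences and washout would have to be written in as well.

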## 2.1 List of Abbreviations

AE	Adverse Event
BMI	Body Mass Index
eCRF	Electronic Case Report Forms
EDC	Electronic Data Capture
HR	Heart Rate
Ig	Immunoglobulin(s)
IRB	Institutional Review Board
PI	Principal Investigator
SAE	Serious Adverse Event
SOPs	Standard Operating Procedures
US	Unites States of America
VO2	Maximal Volume of Oxygen (Consumed)
WHO	World Health Organization

### 3.1 Introduction

The current national incidence rate of obesity in America is 118 million adults (36.5%), based on Body Mass Index (BMI) > 30 [1,2]. The cost of the Obesity Disease is over \$150 Billion dollars in the USA last year, and the CDC states that “The medical costs for people who have obesity were \$1,429 higher” (than non-obese adults). The demographics for American obesity can be seen in Figure 1, and the greatest percentage by ethnicity is among non-hispanic black Americans and obesity is greatest in the 40-59 age group.[1] The WHO estimated that the United States is the fattest country on the planet.

Hidden food allergies are estimated to affect up to 75% of the US population [3-5]. While food allergy testing and elimination have been studied for reduction of migraine headaches and intestinal disorders, the research has not been extensive in determining the efficacy of food allergy elimination in obesity reduction [3-11]. Many weight loss protocols have been examined [6-41] but studies identifying and reversing the causes of obesity are few. Without identification and reduction of the cause, protocols only treat the symptoms.

However, one definitive, food allergen elimination study for over-weight reduction was conducted by Lewis et al [6]. They tested 120 overweight subjects (mean age 45.5, BMI = 29) for IgG food allergens and foods that had a positive reaction were removed for experimental subjects diet for 90 days. These subjects saw significant changes in weight and waist/hip circumferences, and the mean changes are as follows: Weight (- 5kg, P<0.01) and Waist circumference (-5.4cm, P<0.01). However that study did not use leukocyte testing to also measure reactions from IgE an IgA, nor did it test other protocols for weight reduction, and the subjects were not all obese [6].

“PAN-5” is an effective combination of separately proven protocols and the acronym includes the following: **P**ortion sized meals (<2 cups, 5/d) [12-14], **A**erobic-surge Exercise for 2-minyes, 5/d) [15-39], and **N**atural foods which must be eaten 5 times/day [40-44]. A portion-sized study with adult subjects was completed by Kesman et al who examined 65 obese adults (Mean age 55.8 and BMI > 30 to 40) and their intervention included a Portion-size plate (2 cups) with separations for food groups. After six months there was a significant change between experimental vs control groups (P=0.41) and the mean changes were -2.4% Δ body weight for Portion Plate vs +2.2% Δ body weight for the control group [12].

A landmark study examining the frequency of eating and portion size was done by Iwao et al. on Olympic boxing athlete's weight loss in a two week study. Twelve boxers were separated into two categories, one group ate 6 meals/day (6M) and one group ate 2 meals/day (2M). The exact same daily food quantities were divided into 6 meals or two meals, and all boxers had similar exercise and training regime [14].

Both groups lost weight and while there was not significant difference in the weight change, the 6M group had a 90% greater change in body fat than the 2M group. This study showed that eating smaller portions sizes, more frequently, yielded greater fat reduction in the 6M group [14].

High intensity exercises with brief durations have been a recent addition to the protocols used in weight loss. A study by Fisher et al, titled "High Intensity Interval - vs Moderate Intensity - Training for Improving Cardiometabolic Health in Overweight or Obese Males: A Randomized Controlled Trial" showed resounding evidence supporting this protocol. High Intensity Interval Training (HIIT) vs a common moderate intensity training (MIT) for weight loss were tested in twenty-eight healthy, overweight or obese males, (age 20, BMI 25 - 35) and this study lasted 6 weeks [15].

The HIIT exercise intervention included 20-minute, interval training on a cycle ergometer at 15% of max anaerobic power (four minutes), followed by 85% of max anaerobic power (30 seconds). The interval cycle was ridden four times per exercise session, three times per week. In comparison the MIT group trained at 55% of peak  $VO_2$  for 45-60 minutes of continual cycling, five days/week. The total time training over the 6-week study duration was as follows: HIIT = 360 minutes vs. MIT = 1,350 minutes. Even with a 3.75 times lesser duration in training the, there was only significant difference in one of eight variables.

The mean change in peak  $VO_2$  was greater for MIT (MIT 11% vs HIIT 2.3%,  $P=0.0185$ ), however there was no significant difference (all  $> 0.05$ ) in all of the other outcome measures: Weight mean change ( $\Delta$ ) was -0.9kg; BMI ( $\Delta$  was -0.29); Total Cholesterol ( $\Delta$  was -10.8mg/dL); Triglycerides ( $\Delta$  was -26.4mg/dL); HDL ( $\Delta$  was -1.65mg/dL); LDL ( $\Delta$  was -6.08mg/dL); Insulin Sensitivity ( $\Delta$  was -0.71). HIIT was almost equal to all changes vs MIT, even though HIIT only required 27% of the time dedicated to exercise vs MIT. Brief high intensity exercise should increase compliance.

A new, brief Aerobic-surge protocol includes exercising at  $\geq 75\%$  of a deconditioned person's estimated maximum heart rate for only two minutes, (5/day) and this formula is  $(220 - \text{age}) \times .75 = \text{target Aerobic-surge heart rate}$ . This brief 2-minute bout was performed five times/day and was tested in a randomized, controlled, multi-centre trial by Willis et al [16]. Fifty four obese subjects (mean age 39, BMI > 30) completed participation at three sites in this 60-day trial. The Aerobic-surge subjects (N=23) were taught how to elevate their HR to the target heart rate ( $\geq 75\%$  of max HR) and measure this from their carotid pulse. The exercises used included stationary bicycling, stair climbing, and other similar exercises to elevate their HR to the target rate. In comparison the Control subjects (N=23) were simply told to "exercise more" which is a common instruction given in primary care.

The dependent variables in that study were changes in weight (pounds) and 'Body Summation' of 10 girth measurements (neck, shoulders, waist, hip, etc.). A 2x2 ANOVA was used to calculate differences. There was a significant difference between groups ( $P < 0.0001$ ), and the mean changes were as follows: Exp = -18.0lbs and -18.7" vs. Control +1.3lbs and +1.7." [16]

Eating natural, unprocessed foods was discussed in a portion size study [13] and Polsen et al examined differences from changing one's diet to natural foods in the New Nordic Diet [40]. They compared the 'Average' diet (control) to the New Nordic Diet (NND) which removed the processed foods and substituted with natural foods (high in fruits, vegetables, fish, and whole grains). In that study 181 obese subjects (mean age 42) were randomly selected to either the NND group or the Average diet for 26-weeks.

The dependent variable was change in weight and there was a significant difference for the NND vs Average group. The NND subjects showed a mean change of -4.7 kg vs the Average group lost only a mean -1.5kg ( $P < 0.001$ ). There were also significant differences seen in Fat change (1.87% difference,  $P < 0.001$ ), Waist circumference (-2.94cm difference,  $P < 0.001$ ), and in Systolic blood pressure (-5.13 mm Hg difference,  $P < 0.001$ ) [40].

These studies show the overlapping benefits from reducing Portion sizes (with greater meal frequency) and Aerobic-surge or brief, high intensity exercise, plus the benefits of eating Natural foods. The **purpose** of this study was to determine if removing food allergens alone or combined with a multi-discipline weight loss protocols are effective in obesity reduction.

This proposed study will have two volunteer, unrandomized groups: Food Allergen elimination (alone) vs. Combined Treatment (Food Allergen elimination + PAN-5). After 90-days the changes will be tested and compared.

### Prevalence of Obesity

The current national incidence rate of obesity in America (36.5% or 118 million adults) and they are obese based on Body Mass Index (BMI) > 30 [1,2].

### Diagnosis of Obesity

Diagnosis of obesity is done with the Body Mass Index scale and readings over 30.

The formula for BMI is:  $\text{Body Weight (kg)} \div \text{Height}^2 \text{ (m)} = \text{BMI}$

### Current Standard of Care for Obesity

The current standard of care for obesity includes medication such as phentermine, dietary food reductions and/or products, calorie reduction, and eventually gastric surgery bypass or sleeve insertions. However none of these treatments address or reduce the cause of this disease.

## **3.1 Summary of Potential Risks**

This is a randomized, cross-over study that will not include and invasive treatments methods or pharmaceutical products. The risks in this study are as follows:

- Drawing blood for diagnostic testing by venipuncture is an invasive procedure that may occasionally be associated with adverse events such as pain, bleeding, syncope, or ecchymosis.
- The Aerobic-surge, 2-minute exercise bouts will have potential risks for injuries such as falls, scrapes, bruises, pulled connective tissue injuries, etc. However this risk is no greater than the risk in daily ambulation and activity.

### **3.2 Summary of Potential Benefits**

The potential benefits include the benefits seen in a Pilot study of food allergy elimination plus addition of this Aerobic-surge exercise as seen in a pilot study [46]:

- Reduction in Weight and BMI
- Reduction in Body Fat percentage
- Reduction in Blood Pressure
- Reduction in Total Cholesterol
- Reduction of Triglycerides
- Reduction of LDL
- Reduced health care expenses
- Improved HDL/LDL ratio
- Improved repertory rate
- Increased energy
- Improved self-image

#### **4                   STUDY OBJECTIVES**

The **purpose** of this study was to determine if removing food allergens alone or combined with a multi-discipline weight loss protocols are effective in obesity reduction.

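### The protocol is labelled randomized, cross-over and case/control but describes two self-selected groups that both eliminate allergens, so its effectiveness objective cannot be answered

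*Protocol*

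**What the plan says.** **Objective.** The Synopsis, the end of the Introduction and Section 4 give the same purpose: to "determine if removing food allergens alone or combined with a multi-discipline weight loss protocols are effective in obesity reduction".

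**Labels.** The Synopsis has "METHODOLOGY: Randomized, Controlled, Cross-over Trial", although its entry "Randomized Categorization" reads only N/A. The Summary of Potential Risks says "This is a randomized, cross-over study that will not include" invasive treatments or drugs. Section 5.3 says "This is an Investigator-Initiated, preliminary case/control study", and Section 5.1.1 uses the same case/control label.

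**Design described.** The Introduction states "This proposed study will have two volunteer, unrandomized groups: Food Allergen elimination (alone) vs. Combined Treatment (Food Allergen elimination + PAN-5". Section 5.1.1 has the same two regimens, "comparing food allergen elimination and food allergen elimination with PAN-5 for metabolic acceleration". Under Section 7.2 all subjects are allergen-tested and "they can volunteer to also be treated with the PAN-5 protocol". Section 7.3 rules out both blinding and randomization. Sections 5.2.1 and 5.2.1.3 follow subjects for 90 days and then treat the study as complete. Sections 5.2 and 11.2 call it a pilot.

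**The concern.** Whether a regimen is effective is a question about a contrast: change under the regimen against change without it. Elimination is common to both groups here, so it has no contrast. The combined regimen has none either, because its only comparator also eliminates reactive foods.

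The labels hide this. Someone who reads only the Synopsis sees a randomized, controlled cross-over trial with an effectiveness objective, and would take a fall in weight as randomized evidence. The case/control label does not fit either, since the groups are formed by chosen treatment and not by outcome. At stake is a conclusion that elimination works, or does not work, with no comparison against people who kept their usual foods.

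**Working it through.** The protocol gives no figure to reproduce on this point. The check is which contrasts the described design can estimate, and whether the protocol's own citations suggest that the gap matters.

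**1. Labels against conduct**

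| Property | Where claimed | What the design sections describe |
|---|---|---|
| Randomized | Synopsis; Summary of Potential Risks | Volunteer groups (Introduction, 7.2); no randomization (7.3) |
| Cross-over | Synopsis; Summary of Potential Risks | No sequence, switch or second period; complete at 90 days (5.2.1.3). The only washout, 30 days in the Synopsis, is an entry rule |
| Case/control | 5.1.1; 5.3 | Groups defined by treatment, not by outcome |
| Controlled | Synopsis | A concurrent, non-randomized comparator, for adding PAN-5 only |

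**2. What can be estimated**

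For mean 90-day change, write D for what would have happened anyway (natural change, regression to the mean, staff contact), E for the effect of elimination, P for the effect of adding PAN-5 to elimination, and S for differences between those who volunteer for PAN-5 and those who do not.

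- Elimination-only group: D + E
- Combined group: D + S + E + P
- Combined minus elimination-only: P + S

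E never appears without D, and E + P never appears without D + S. The between-group difference cancels E and leaves P mixed with S. No analysis of these data separates them without outside assumptions.

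A true cross-over between these two regimens would not help with the objective. Each subject would contribute one period containing E and one containing E + P, so E would again cancel.

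**3. How comparison groups moved in the studies that the Introduction cites**

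- Natural-foods diet study, 26 weeks: intervention -4.7 kg, comparison -1.5 kg. Controlled difference: -4.7 - (-1.5) = -3.2 kg. Before-after change alone overstates this by 4.7/3.2 - 1 = 47%.
- Aerobic-surge study, 60 days: intervention -18.0 lb, comparison +1.3 lb. Controlled difference: -18.0 - 1.3 = -19.3 lb. Before-after change alone understates this by 1.3 lb.

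Scaled to 90 days, assuming linear change:

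- -1.5 kg x 90/182 = -0.74 kg
- +1.3 lb x 0.4536 kg/lb x 90/60 = +0.88 kg

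Against the -5 kg cited for 90 days of elimination: 0.74/5 = 15% and 0.88/5 = 18%.

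These are rough proxies for D. One comparison group followed an average diet and the other was told to exercise more. The Introduction also reports the 60-day study inconsistently: 54 completers, but two groups of 23, and 23 + 23 = 46. The figures show that D need not be zero and can take either sign. They do not estimate D for this trial.

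**The case against.** **Non-randomization is disclosed.** The Introduction and Sections 7.2 and 7.3 agree on how subjects are assigned, and the Synopsis has its N/A entry. This stands as far as it goes: assignment is not ambiguous to someone who reads the whole protocol. It is also what makes the labels in the Synopsis and the Summary of Potential Risks wrong.

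**It is a pilot with no success criterion.** A pilot may reasonably have no elimination-free group, and a reader might infer that its absence is itself the error. The documents do not support that. The error is that the objective asks for what this design cannot give, and pilot status does not change that.

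**Controlled is not empty.** Correct. The elimination-only group is a concurrent comparator for adding PAN-5, so it would be too strong to say that the whole Synopsis label is false. The word fails for elimination alone and for the combined package, which are what the objective names.

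**Six months of contact could mean a second period.** Sections 11.5 and 11.6 might suggest one, but no switch is described, and a switch between these regimens would still include no elimination-free period.

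**Section 5.3 breaks off in the text at hand.** Any limitation stated there cannot be seen. Lost text would not undo Section 7.3 or the group definitions.

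Two further inferences should be resisted. The 0.05 level in Section 11.8.5 only sets a threshold, and its interpretation may properly be left to an analysis plan. The exercise demonstration in Section 8.1 without a named group is at most missing detail.

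**Conclusion.** The point holds as wrong in the current text, and an analysis plan could not settle it. Randomized, cross-over and case/control have no support in the described conduct. Controlled holds only for a non-randomized comparison of adding PAN-5. Whether elimination, alone or combined, is effective cannot be answered.

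This follows from the structure and needs no assumed effect, SD or group size. The cited comparison-group changes, roughly -0.7 to +0.9 kg over 90 days under linear scaling, indicate only that before-after change can err in either direction. The self-selection term S cannot be sized from the document.

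This does not make the study worthless. It can describe change in each group and give an exploratory estimate of the PAN-5 increment.

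**What to change.** 1. **Labels.** In the Synopsis, the Summary of Potential Risks and Sections 5.1.1 and 5.3, replace every design label with *non-randomized two-group pilot study*.
2. **Objective.** In the Synopsis, Introduction and Section 4, restate it as: *to describe 90-day change in weight, Fat% and BMI in each group, and to estimate the combined-minus-elimination-only difference as an exploratory comparison subject to self-selection*. Add that no conclusion will be drawn that elimination or the combined regimen is effective.
3. **Separately, reconcile duration and contact.** Sections 5.2.1 and 5.2.1.3 end the study at 90 days. Section 5.2.1.1 has daily contact for 30 days and weekly contact to three months, and Section 7.4 has daily tracking through 90 days. Sections 11.5 and 11.6 have two months of daily contact and then weekly contact to six months. These passages must be made to agree.

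The cost is a wording amendment, with the approvals that Section 12.3 requires and no added subjects or visits. The downside is that the study can claim less. Keeping the effectiveness objective would instead need a concurrent elimination-free comparator, preferably randomized, which is a different and larger undertaking.
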